7.11 ECG Procedure

A standard 12-lead ECG will be recorded after 5 minutes in a supine position. The Investigator (or designee) will interpret the ECG's by use of an electronic measurement using the following categories: within normal limits, abnormal but not clinically significant, or abnormal with clinical significance. ECG's are performed according to the SOE ([Appendix A](#)). The following parameters will be recorded from the subject's ECG trace: heart rate, QT interval, PR interval, QRS interval, RR interval, and QTc (corrected) using the Fridericia correction ($QTcF = QT \div \text{cube root of the R-R interval}$ [where R-R is the duration of the entire cardiac cycle]).

When ECGs are to be collected at the same time point as a blood collection, ECGs should be collected first to avoid any artificially increased heart rates due to the blood collection.

On clamp days, ECGs will be performed at baseline which is 15 min (± 5 min) prior to dosing, at 5 min (± 3 min), 60 min (± 10 min), 180 min (± 20 min) and 720 min (± 30 min) post-dose.

ECGs will be performed at days indicated in the SOE ([Appendix A](#)).

In some cases, it may be appropriate to repeat abnormal ECGs. If a machine-read QTc value is prolonged, repeat measurements may not be necessary if the Investigator's interpretation determines that the QTc value is in the acceptable range.

7.12 Fasting Plasma Glucose

Fasting plasma glucose will be measured during the in-clinic period with an YSI 2300 STAT glucose analyzer at time points stated in the SOE ([Appendix A](#)).

7.13 Standardized Meals

At each period, the importance of maintaining the body weight within a 5% range throughout the study will be explained. The counseling for each subject will be individualized based on their actual measured body weight. Additionally, subjects will be counseled to maintain their normal diet and exercise regimen. They will be instructed not to start any new diets, supplements, or exercise programs during the study.

During in-house period(s), subjects will receive standardized meals. Meal will be provided after the clamp procedure has been terminated.

7.14 Euglycemic Glucose Clamp

7.14.1 Biostator® Overview

The Biostator Automated Glucose Analyzer (MTB Medizintechnik, Amstetten, Germany) is a 510(k)-cleared device that automates the glucose clamp technique providing continuous assay of blood glucose measurements and minute-by-minute adaptations of glucose infusion rates (GIR).

In the clamp scenario, the Biostator automatically calculates and infuses the appropriate amount of Dextrose 20%, based on the actual measured blood glucose and its deviation from target level. The Biostator analyzer, using an internal algorithm, makes minute by minute adjustments to GIR, as necessary, to keep the blood glucose concentration at the target level. Adjustments are done per current blood glucose measurement and the variability observed during the last five readings.

7.14.2 Glucose Clamp Set-Up

The Biostator is set up with infusion lines for blood glucose management. One 0.9% sodium chloride (NaCl) and two Dextrose 20% (D20) IV infusion lines are connected via an infusion module. All three lines are linked together using three-way valves which are then connected to the subject through an IV catheter on the contralateral arm (contralateral and ipsilateral are defined as relative to Biostator). A second IV line is inserted (generally the dorsal hand vein, the lateral wrist vein of ipsilateral arm or any peripheral arm vein) and setup through a different Biostator module using a Double Lumen Catheter (DLC). One lumen is used for a continuous blood sample draw at an estimated rate of 2 mL/hr; while the other lumen, is used to infuse a low concentration of heparinized saline solution to the catheter tip where it is then mixed with the blood drawn. This mix avoids sample clotting within the tubing. The DLC vein site is covered by a heating pad for arterialization of venous blood flow. The Biostator system programming and operation is done per [REDACTED] standard operating procedures. An external D20% IV line is connected to the infusion lines. This infusion is manually operated by the technicians running the clamp in coordination with the medical staff and is used (e.g., in case the GIR delivered by the Biostator is insufficient).

As a background validation with a second methodology for safety, the standardized measurements of the Biostator will be verified on a regular basis using the YSI reference (YSI 2300 STAT or equivalent YSI Glucose Analyzer; Yellow Springs Instruments, Ohio, USA) device at approximately every 30 minutes.

Please see [Appendix B](#) for a detailed Clamp Sampling Schedule.

7.14.3 Glucose Clamp Procedure

During the study, subjects will undergo two euglycemic clamp procedures, one per treatment period. All clamp procedures will be performed identically.

Subjects will be connected to the Biostator through peripheral arm veins as described in section 7.14.2. The clamp procedure will follow instructions described in section 4.2.

The Biostator will be turned on and programmed. The body weight in kilograms used for Biostator programming on both clamps, corresponds to the weight measurement obtained on Day 1 of Treatment Period 1. At least one hour before dosing ($t = -60$ min), the Biostator will start recording data. During this pre-dose monitoring period, glucose readings are obtained and analyzed with a YSI 2300 STAT or equivalent YSI Glucose Analyzer (Yellow Springs Instruments, Yellow Springs, Ohio, USA) at the following time points relative to the start of the trial drug infusion: -60, -30, -20 and -10 minutes. The average of blood glucose values prior to dosing (-30 min, -20 min, -10 min) correspond to each subject's individual BASELINE glycemic level. The glucose CLAMP TARGET level is determined by subtracting 5 mg/dL from the BASELINE glycemic level (Target level = BASELINE - 5 mg/dL). Subjects whose differences between initial fasting BG values (-30, -20, -10 min) exceed the limit of 10 mg/dL will be rescheduled to another day. Additionally, subjects will not be dosed if mean fasting plasma glucose is < 75 mg/dL due to proximity to overt hypoglycemia or > 99 mg/dL. Subjects may be re-scheduled once to come back to the site on a later day and may be dosed if the mean fasting plasma glucose is ≥ 75 mg/dL or ≤ 99 mg/dL prior to dosing.

At $t = 0$ -min, the investigational product will be administered per randomization schedule.

After dosing, the onset of insulin action will be identified by a ≥ 5 mg/dL decline of glucose concentration from the baseline level. After the onset of insulin action is identified, glucose infusion will then be utilized as needed to maintain the target level ($\pm 10\%$) using a variable infusion of D20%. This GIR is calculated and infused by the Biostator. The glucose infusion is continuously diluted with saline solution at an approximate rate of 30 ml/hour to avoid the remote possibility of localized pain or venous thrombosis as complications. In case a high GIR is necessary, a part of the glucose infusion will be given by an external infusion pump. The infusion rate provided by the external pump will then be added to the infusion rate of the Biostator.

The subjects will remain fasting and in a supine or semi supine position during the entire glucose clamp. The subjects are allowed to sip water throughout the trial and will otherwise remain fasting.

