4.3 Rationale for Study Design and Endpoints

A single dose cross-over design is chosen in order to allow each subject to act as his/her own control in order to reduce variability.

A minimum 7-day wash-out period before and between the two treatment periods is introduced to ensure a sufficient wash-out from previous dosing, in order to avoid any carry-over effects.

Randomization is used to avoid bias introduced through an association between trial drug allocation order and subject characteristics.

Blinding of participants and personnel is introduced in order to avoid performance bias.

Due to the variability in fasting blood glucose concentrations in subjects with type 1 diabetes, which might affect the metabolic response to the study drug, healthy subjects have been chosen. A study in healthy subjects is likely to produce less PK variability compared with that in patients with potentially confounding factors such as underlying and/or concomitant disease and concomitant medications. C-peptide and endogenous human insulin in parallel to the insulin aspart concentration is measured during the study, to detect potential changes in endogenous insulin secretion and enable a correction for endogenous insulin secretion, if necessary.

Enrollment criteria will favor a generally insulin-sensitive population and diseases/conditions and medications associated with insulin resistance have been excluded.

The sample size of 60 subjects is chosen as it represents a typical number for a biosimilar study. The use of the euglycemic glucose clamp method is chosen to assess PD in a standardized fashion and for safety reasons to avoid hypoglycemia.

Glucose levels below approximately 60 mg/dL must be avoided because they result in the

stimulation of counter regulatory hormones (epinephrine, glucagon, cortisol, growth hormone) to increase blood glucose concentrations and lead to a rapid and pronounced worsening of insulin sensitivity, thus influencing the estimated time-action profile of the investigated insulin preparation. Therefore, blood glucose (BG) inclusion criterion prior to the clamp is limited to a fasting plasma glucose value ≥ 75 mg/dL (for the mean of the $-30 \leq$ to -10 min glucose measurements), as the target clamp level is 5 mg/dL below the mean fasting BG values. The chosen target level of mean fasting glucose minus 5 mg/dL will ensure that endogenous insulin secretion is sufficiently suppressed and will not interfere with PK and PD assessments.

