5.3 Prohibited Medications

Use of prescription or nonprescription drugs is prohibited from 7-14 days prior to dosing.

Vitamins, mineral supplements, occasional paracetamol and /or birth control methods are allowed after discretion of the Investigator. Desogestrel is not allowed.

5.4 Check-in Criteria on Day 1

Subjects will be educated about the factors that may influence insulin sensitivity, such as refraining from strenuous exercise within 72 hours prior to the injection of the investigational product and during the in-house period, avoidance of alcohol and herbal supplements within 24 hours prior to dosing, caffeinated drinks (caffeine containing food and beverages within 24 hours prior to dosing), smoking or medication and illness/infection.

Treatment Period 1

At check-in for Treatment Period 1, subjects will not be allowed to check in if they meet any of the following criteria and the treatment period may be rescheduled one time with a time window of 1-14 days.

- (1) Positive alcohol breath test.
- (2) Positive urine drug screen test.
- (3) Positive urine pregnancy test in female subjects. If sample is positive, blood sample will be sent to local lab for confirmation. A negative test result is mandatory prior to dosing.
- (4) Any medical condition that could interfere with glucose metabolism, as judged by the Investigator.
- (5) Any use of medicine (prescribed or over-the-counter) other than any allowed concomitant medications within the last 7-14 days prior to dosing.
- (6) Strenuous exercise within the last 72 hours prior to injection of the investigational product.
- (7) Consumption of caffeine containing food and beverages within 24 hours prior to dosing.

On Day 1, subjects will not be allowed to be dosed if they meet the following criterion and the treatment period may be rescheduled one time with a time window of 1-14 days.

- (1) Subjects whose differences between initial fasting blood glucose values (-30, -20, -

10 min) determined by the YSI exceed the limit of 10 mg/dL or whose mean FPG is < 75 mg/dl or > 99 mg/dL will be rescheduled.

Treatment Period 2

At check-in for Treatment Period 2, subjects will not be allowed to check in if they meet any of the following criteria and the treatment period may be rescheduled one time (1-14 days later). The Sponsor will be notified about the rescheduling in a timely manner.

- (1) Positive alcohol breath test.
- (2) Positive urine drug screen test.

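### The rule for dosing at a rescheduled visit joins its two glucose limits with 'or', so it excludes no value and contradicts the no-dose rule beside it; it should say 'and'

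*Protocol*

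**What the plan says.** Before each clamp, the mean of the glucose readings at -30, -20 and -10 minutes decides whether the subject may be dosed. The same mean less 5 mg/dL becomes the clamp target.

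Protocol 7.14.3 gives two consecutive rules on that mean:

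- The bar: "subjects will not be dosed if mean fasting plasma glucose is < 75 mg/dL due to proximity to overt hypoglycemia or > 99 mg/dL".
- The return visit: the subject may be rescheduled once and "may be dosed if the mean fasting plasma glucose is ≥ 75 mg/dL or ≤ 99 mg/dL prior to dosing".

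The same pair of sentences appears in the synopsis under IV(2) PD Glucose Clamp and in section 4.2 Study Description.

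Two other sections bear on the range:

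- Section 5.4, Check-in Criteria on Day 1, repeats the bar for Treatment Period 1 and again for Treatment Period 2: subjects "whose mean FPG is < 75 mg/dl or > 99 mg/dL will be rescheduled".
- Section 4.3 explains the lower limit. The "blood glucose (BG) inclusion criterion prior to the clamp is limited to a fasting plasma glucose value ≥ 75 mg/dL", because the target lies 5 mg/dL below the fasting mean and "Glucose levels below approximately 60 mg/dL must be avoided".

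**The concern.** The bar forbids dosing below 75 or above 99 mg/dL. The matching permission is at least 75 **and** at most 99. When a condition of the form 'A or B' is negated, the 'or' has to become 'and'. The return-visit sentence reverses the two inequalities but keeps the 'or', so it permits every value, including all those the previous sentence forbids.

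The sentence is operative text. It is written for the return visit, when the single permitted rescheduling has been used and staff must decide whether to inject insulin into a healthy volunteer. Someone who consults only that sentence finds a condition that is always met, while the adjacent sentence and section 5.4 say the opposite. Section 7.14.3 also refers the reader to section 4.2 for the clamp instructions, and section 4.2 carries the same wording, so the cross-reference does not resolve the conflict.

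A subject dosed below the floor would be clamped at a correspondingly lower target, closer to the level at which, according to section 4.3, counter-regulatory hormones distort the time-action profile.

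**Working it through.** The plan gives no figure to reproduce. The check is a logical one on the stated limits, followed by the clamp targets they imply.

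**1. Inputs**

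| Rule on the fasting mean x (mg/dL) | Where |
|---|---|
| Do not dose if x < 75 or x > 99 | Synopsis IV(2); 4.2; 7.14.3; 5.4 (Periods 1 and 2) |
| Return visit: may dose if x ≥ 75 or x ≤ 99 | Synopsis IV(2); 4.2; 7.14.3 |
| Pre-clamp value must be ≥ 75 | 4.3 |
| Target = baseline − 5, held within ±10% | 4.2; 7.14.3; SAP 4.3 |
| Avoid levels below about 60 | 4.3 |

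**2. Logic**

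- As written: {x ≥ 75} ∪ {x ≤ 99} is all x. Any value under 75 meets the second part, and any value over 99 meets the first.
- With 'and': {x ≥ 75} ∩ {x ≤ 99} is 75 to 99, exactly the complement of the bar.

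**3. Numerical confirmation**

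The rules were evaluated for glucose from 0 to 400 mg/dL in steps of 0.1, which gives 4,001 values.

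| Condition | Values meeting it | Of these, forbidden by the bar |
|---|---|---|
| Bar: < 75 or > 99 | 3,760 | n/a |
| Return visit as written ('or') | 4,001 | 3,760 |
| Return visit with 'and' | 241 | 0 |

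The 241 permitted values and the 3,760 barred values add up to 4,001, with no gap and no overlap. Individual values behave as follows:

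| x | Barred? | Permitted with 'or'? | Permitted with 'and'? |
|---|---|---|---|
| 60 | yes | yes | no |
| 74.9 | yes | yes | no |
| 75 | no | yes | yes |
| 99 | no | yes | yes |
| 99.1 | yes | yes | no |
| 130 | yes | yes | no |

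**4. What the intended limits protect**

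- Targets over the intended range: 75 − 5 = 70 and 99 − 5 = 94 mg/dL.
- Lower edge of the control band at the floor: 70 × 0.90 = 63.0 mg/dL.
- Upper edge at the ceiling: 94 × 1.10 = 103.4 mg/dL.
- Baseline at which the lower edge reaches 60 mg/dL: 60 / 0.90 + 5 = 71.7 mg/dL.
- Margin left by the floor: 75 − 71.7 = 3.3 mg/dL.

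These last figures describe how tight the intended floor is. They do not measure the effect of the slip, which depends on whether anyone would follow the faulty sentence over its neighbours.

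**5. Would the analysis catch such a clamp?**

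Not automatically. The four criteria for the PD per-protocol population in SAP 6.1.1 do not include baseline glucose, and the severe deviations named in SAP 6.3.2 do not list it. That list is expressly not exhaustive, so the Management Review Board could still exclude the data.

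**The case against.** The strongest reply is that the protocol already handles this. In all three places the faulty sentence directly follows a mandatory bar that is not limited to first visits, and a permission does not cancel a prohibition stated one sentence earlier. Section 5.4 sets the correct limits for Day 1 of both periods and exempts no rescheduled Day 1. The 'or' can even be given a sense: a subject turned away for a low value may return once at or above 75, and one turned away for a high value once at or below 99. Added to the standing bar, that yields 75 to 99. Other safeguards limit harm: continuous surveillance and treatment rules for hypoglycemia (8.3.1.1), and reference glucose checks about every 30 minutes (7.14.2).

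Most of this stands. The whole protocol does prohibit out-of-range dosing, its intent is not in doubt, and a careful site would apply 75 to 99. The ±10% band is a control range and the 60 mg/dL limit is approximate, so 63 mg/dL is not a predicted lowest value.

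It does not make the sentence right. The charitable reading works only by importing the limits from other text. A stated dosing threshold should not depend on its neighbours to mean anything, least of all in the sentence written for the return visit and repeated in the section to which 7.14.3 points.

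**Conclusion.** The sentence is wrong as written in three places and should be corrected. It is an inconsistent statement at a dosing gate, not a missing gate: the adjacent bar, section 5.4 and the rationale in section 4.3 together fix the intended range at 75 to 99 mg/dL. Read alone, the sentence permits all values, including every value the bar forbids; with 'and' the conflict disappears completely.

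The practical effect should be small. It would arise only if site staff followed this sentence over the text around it, and the documents give no basis for estimating how often that would happen. No sample size, error rate, endpoint definition or primary analysis changes. The correction is worth making because the threshold governs insulin dosing in healthy volunteers and the same glucose mean sets the clamp target.

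The conclusion that this is a slip rather than a deliberate relaxation for returning subjects rests on the consistent limits everywhere else. Nothing in the protocol suggests that a wider range was meant at the second attempt.

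**What to change.** In the synopsis (IV(2) PD Glucose Clamp), section 4.2 and section 7.14.3, change 'or' to 'and' between the two limits of the return-visit sentence, and change 'if' to 'only if', so that dosing is allowed only when the mean is both ≥ 75 and ≤ 99 mg/dL. Leave sections 4.3 and 5.4 as they are.

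The cost is the same short wording correction three times. Design, sample size and analysis are unaffected.

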7.14.4 Glucose Clamp Quality Parameter

The quality of the clamp data will be reviewed on a regular basis by the PI and the clamp supervisors at regularly scheduled Data Review Meetings. The following parameters are included in the review:

- Clamp coefficient of variation (CV): Coefficient of variation of device BG measurements calculated by the following formula:

$$(\text{SD of Device BG} / \text{Mean Device BG}) * 100$$

- Clamp deviation from the target (DFT): Mean difference (mg/dL) between device and target BG level represented as a percentage, calculated as follows:

$$[\text{Mean (device BG} - \text{target level)} / \text{target level}] * 100$$

- Accuracy: Mean difference of all paired BG measurements of device vs reference method represented as a percentage.

Calculations for CV and DFT will be based on each clamp from the minute that the glucose infusion rate is initiated (Start of GIR) to the minute that the glucose infusion rate is no longer required (End of GIR) or at the end of the clamp at the 12-hour mark, whichever appears first. Note that an End of GIR is not necessarily an end of the clamp.

In case a subject's GIR requirement is intermittent or has interrupted periods during the clamp, the PI will review the clamp data and determine how the clamp quality will be calculated.

Generally, overall mean clamp CV and DFT for the clamps should be less than 10%. If the calculated CV or DFT for an individual clamp is $\geq 12\%$, the clamp data for that clamp should be considered for exclusion from the final data analysis and the clamp should be repeated (if possible), or the subject should be replaced, following discussion between the Investigator and the Sponsor. If the accuracy calculation is $> 12\%$ but the CV and DFT are $< 12\%$, it will be at the discretion of the Principal Investigator to determine if the clamp data quality is acceptable. [REDACTED] Clinical Data Management Team and the Sponsor will also be consulted.

7.15 Pharmacokinetic Assessments and Schedule

Blood for PK analysis of the IP, the human insulin analog, will be collected at the time points indicated in the SOE ([Appendix A](#)) and follow the PK blood sampling schedule below.

At each sampling time point, 1.0 mL of blood will be discarded for waste (utilizing a throw away tube). Thereafter, one 6.0 mL whole blood sample per scheduled time point will be collected to provide a minimum of 1.5 mL of serum for PK measurements and 1.5 mL of serum as a secondary back-up sample. Instructions for sample processing and shipment are provided below.

Table 7-2 PK Blood Sampling Schedule (6 mL per sample)

Seq. #	Scheduling	Time window	Sample No., "XX"	#	Scheduling	Time window	Sample No., "XX"
1	-60 min	± 5 min	01	15	75 min	±3 min	15
2	-30 min		02	16	80 min	±5 min	16
3	0 min	±1 min	03	17	90 min		17
4	5 min		04	18	105 min		18
5	10 min	±2 min	05	19	120 min		19
6	20 min		06	20	150 min	±10 min	20
7	25 min	±3 min	07	21	180 min		21
8	30 min		08	22	210 min		22
9	40 min		09	23	4 h		23
10	50 min	±3 min	10	24	5 h	±20 min	24
11	55 min		11	25	6 h		25
12	60 min		12	26	8 h		26
13	65 min		13	27	10 h		27
14	70 min		14	28	12 h		28
Total							28 (168mL)

PK Sample Processing and Shipment Instructions are described below:

(1) Sampling Procedure

A catheter will be inserted into one of the antecubital region veins for blood sampling. Alternatively, collection from a vein from the hand or forearm for easier access or via venipuncture is also acceptable. PK blood draws should use the opposite arm of the glucose infusion/clamp. Preferably, the arm with better venous access will be used for PK samplings, and the opposite arm for the glucose infusion/clamp. In case of extraordinary situations, such as IV infiltration etc, the PK samples could be collected from the arm of the clamp, for safety reason.

After each blood sample collection, a catheter flush will be performed to avoid catheter clot formation and prevent interference between samples.

At each PK sampling point, the first 1 mL of blood will be discarded for waste (utilizing a disposable tube), and blood samples (~6 mL per sample), will be collected in a serum separation tube and left to stand at room temperature for 30 - 60 minutes. Each sample will be centrifuged at 2-8°C, 1,000-1,300 g for 20 minutes.

Isolated serum will be distributed into two (2) 2.0 mL cryo vials, approximately 1.5 mL in the first aliquot and the remainder in the second aliquot. The serum samples will be frozen on dry ice and then immediately (within 60 minutes following serum isolation) stored in a freezer at -20°C or lower

until analysis.

(2) PK Sample ID

The sample ID for PK blood samples (before centrifugation) is defined as:

“I4-B-nn-v-XX”

where **I4-B** represents study for “I004 Study B”, **nn** is the subject ID, **v** is the treatment period/visit number and **XX** is the two-digit time-point sequential number of the sample: 01, 02, 03, ...28 as listed in Table 7-2.

The sample ID for PK samples (after centrifugation) is defined as **“I4-B-nn-v-XX-k”** and **k** is the aliquot number (A or B). The PK sample ID labels, with the size of “1/2” × 1 3/4” (Avery label 5667), should be printed in black font as demonstrated below:

“I4-B-nn-XX-k”

(3) Sample Transportation

Prior to sample transportation, all samples should be stored in a box and must be organized in sequential order by subject and separated by aliquot. The chain of custody, temperature control and related documents for sample transportation must be recorded. During transportation of PK samples from the site to Amphastar, the temperature should be below -20°C.

(4) Bioanalytical Methods of Insulin Aspart

An automated, high-throughput method for targeted quantification of Insulin Aspart (I004) in human serum includes (i) mass spectrometric immunoassay (MSIA) for immune-enrichment which is based on the Thermo Scientific™ MSIA™ platform and (ii) analysis by UPLC with high resolution mass spectrometer (UPLC/HRMS) will be performed.

MSIA™ platform approaches based on immune-enrichment prior to the mass spectrometric determination, using the insulin antibodies immobilized on a solid support first to capture the molecule of interest from the matrix, then subsequent washing cycles are used to remove contaminants and finally the analyte is eluted prior to its analysis by UPLC/HRMS.

[figure not shown]
The HR-MS detection provides significant advantages over enzyme linked immunosorbent assay (ELISA) methods because the selectivity of MS allows detection of co-eluting analogs. Full-scan MS data could be analyzed due to the low noise and selectivity of the MSIA extraction technology. Co-eluting insulin analogs were easily separated and identified based on the accurate m/z values of each precursor's charge state and corresponding isotopes.

The results of the method feasibility study indicated the method is accurate with the LLOQ of 50 pg/mL or 0.05 ng/mL with a good linearity over the quantitation range.

(5) Bioanalytical Methods of Endogenous Insulin

Amphastar developed sensitive and specific UPLC/HR-MS method to detect the endogenous human insulin.

Figure 7-1 MSIA Technology Workflow

